Visit Window			$\pm 3d$	$\pm 3d$	$\pm 3d$	$\pm 3d$	± 3d	+ 7d	$\pm 7d$	± 7d
Pregnancy test ¹	Х	Х				Х	Х		Х	
Blood sample for determination of BRCA status via Myriad ^{m,n}	Х									
Blood sample for disease specific marker (CA-125) °		Х				Х	Х	Х		
Tumor Assessment (CT or MRI according to RECIST v1.1)	X ^p	st (± 1	Every 8 weeks (± 1 week) from receipt of first dose of study drug (Visit 2) for 48 weeks and every 12 weeks (± 1 week) thereafter until PD has been determined by the Investigator according to RECIST v1.1 criteria (including confirmatory RECIST scan).							
Adverse events (continuous from the time of informed consent) ^q	Х	Х	Х	Х	Х	Х	Х	Х	Х	
Concomitant medications including blood transfusions	Х	Х	Х	Х	Х	Х	Х	Х	Х	
Olaparib dispensed/returned r		Х				Х	Х	Х		

Table 6

Study Plan - On Study Treatment and Discontinuation

Visit Number	1	2	3	4	5	6	Subsequent on treatment visits every 4 weeks ^a Tumor assessment visits every 8 or 12 weeks ^b Visit No. 7 onwards	Study treatment discontinued ^c	Follow-up 30 days after last dose of study medication ^d	Overall Survival Follow-up °
Day	-28 to -1	1	8	15	22	29	Day 1 of next visit period ^f			4
Visit Window			± 3d	+ 7d	± 7d	± 7d				
Subsequent cancer therapy following discontinuation of study treatment ^s									Х	
Blood sample for pharmacogenetics (mandatory) ^t		X								-
Tumor sample (mandatory) ^m , n,u,v	Х									
CCI										
The second secon										
										X

a. Visit to take place on Day 1 of a 4-week visit period up to 52 weeks (if not progressed and still on treatment), then on Day 1 of a 12-week visit period relative to date of enrollment until PD (RECIST v1.1).
b. Follow-up assessments will be performed at the end of every 8 weeks (± 1 week) up to 48 weeks, then every 12 weeks (± 1 week) relative to date of enrollment until PD (RECIST v1.1).
b. Follow-up assessments will be performed at the end of every 8 weeks (± 1 week) up to 48 weeks, then every 12 weeks (± 1 week) relative to date of enrollment until PD (RECIST v1.1).

Date 10 October 2017

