4.2.4 Study Visit 7, Day 57, and every 4 weeks onwards

Subsequent on-treatment visits for the active treatment period will take place on Day 1 of a 4-week visit period up to 52 weeks (if not progressed and still on treatment), then on Day 1 of a 12-week visit period relative to date of enrollment until PD (RECIST v1.1). Subsequent on-treatment visits for subjects who remain on treatment post-progression should take place every 12 weeks. Tumor assessment visits will be performed at the end of every 8 weeks (± 1 week) up to 48 weeks, then every 12 weeks (± 1 week) relative to date of enrollment until PD (RECIST v1.1). Subjects will be contacted to assess for survival every 12 weeks following disease progression until death, withdrawal of consent, or study closure. See Section 4.4.

The following procedures will be performed at Visit 7, Day 57 (\pm 3 days) and every 4 weeks onward (i.e., Visit 8 [Day 85], Visit 9 [Day 113], etc.) through the active treatment period:

- Assess functional status using the ECOG performance status scale (see Appendix F);
- Obtain blood sample for hematology/clinical chemistry (see Section 5.2.1 and Table 8);
- Obtain blood sample for disease specific marker (CA-125) (see Section 5.2.1.4 and Table 8);
- Assess tumor (CT or MRI according to RECIST v1.1) (see Section 5.1.1);
- Note: The tumor assessments according to RECIST v1.1 will be performed every 8 weeks (± 1 week) from the first dose of study drug (Visit 2) for 48 weeks, and then every 12 weeks (± 1 week) (relative to the date of enrollment) thereafter until determined by the Investigator according to RECIST v1.1 criteria (including confirmatory RECIST scan).
- Assess and record concomitant medications including blood transfusions;
- Assess subject for adverse events (continuous from time of informed consent); and
- Dispense/return olaparib.

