5.1 Efficacy assessments

5.1.1 CT and MRI scans tumor assessments (RECIST v1.1)

The baseline tumor assessment will be performed no more than 28 days prior to study treatment start (Visit 2) and as close as possible to study treatment start. Following the

baseline tumor assessment, subsequent tumor assessments according to RECIST v1.1 should be performed at the end of every 8 weeks (\pm 1 week) from first dose of study drug (Visit 2) for 48 weeks and every 12 weeks (\pm 1 week) (relative to the date of enrollment) thereafter until PD. If an unscheduled assessment was performed and the subject has not progressed, every attempt should be made to perform the subsequent assessments at their scheduled visits. Subjects who are determined to have PD according to RECIST v1.1 criteria (including confirmatory RECIST scan) by the Investigator may have additional scans performed per the site's standard of care. All treatment decisions will be based on the Investigator's assessment of the scans.

A copy of all tumor assessment scans will be collected by an AstraZeneca Representative through disease progression.

All subjects should have RECIST assessments until documented evidence of objective radiological progression in accordance with RECIST v1.1, irrespective of treatment decisions (i.e., RECIST follow-up until progression even if a subject discontinues study treatment prior to progression and/or receives a subsequent therapy prior to progression).

At baseline, the imaging modalities used for RECIST assessment will be CT (MRI where CT is contraindicated) scans of the chest, abdomen, and pelvis, with other regions as clinically indicated for the assessment of disease. Follow-up CT or MRI assessments (per RECIST v1.1) will be by chest (in those subjects with disease in the chest or upper abdomen lymphadenopathy at baseline), abdomen, and pelvis, with any other regions imaged at baseline where disease was present. Any other sites at which new disease is suspected should also be appropriately imaged. The methods of assessment of tumor burden used at baseline must be used at each subsequent follow-up assessment. A CT examination with intravenous contrast media administration is the preferred method. An MRI should be used where CT is not feasible or it is medically contraindicated. For brain lesion assessment, MRI is the preferred method. Subjects must be followed-up until RECIST disease progression.

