Radiological examinations performed in the conduct of this study should be retained at the site as source data.

It is important to follow the assessment schedule as closely as possible. If scans are performed outside of the scheduled visit ± 1 week window interval and the subject has not progressed, every attempt should be made to perform the subsequent scans at their scheduled time points (± 1 week).

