8.4.3.4 Progression-free survival

Progression-free survival is defined as the time from the date of first dose of olaparib until the date of objective radiological disease progression (Investigator assessed via RECIST v1.1) or death (by any cause in the absence of disease progression) regardless of whether the subject withdraws from therapy or receives another anticancer therapy prior to disease progression. Subjects who have not progressed or died at the time of analysis will be censored at the time of the latest date of assessment from their last evaluable efficacy assessment. However, if the subject progresses or dies after 2 or more missed visits, the subject will be censored at the time of the latest evaluable assessment. Given the scheduled visit assessment scheme, 2 missing visits will equate to more than 18 weeks (or 26 weeks after 1 year) since the previous RECIST v1.1 assessment, allowing for early and late visits. If the subject has no evaluable visits or does not have a baseline assessment, they will be censored at Day 1 unless they die within 2 visits of baseline (18 weeks allowing for visit window).

The PFS time will always be derived based on scan/assessment dates and not visit dates. Assessments/scans contributing towards a particular visit may be performed on different dates. The following rules will be applied:

- Date of progression will be determined based on the earliest of the assessment/scan dates of the component that triggered the progression.
- When censoring a subject for PFS, the subject will be censored at the latest of the assessment/scan dates contributing to a particular overall visit assessment.

Overall visit assessments will be determined for each assessment (scheduled or unscheduled) and will contribute to the derivation of PFS.

Objective radiological progression is defined as at least a 20% increase in the sum of the diameters of the TLs (compared to previous minimum sum) and an absolute increase of > 5 mm, an overall non-TL assessment of progression, or a new lesion.

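### PFS censoring: the week conversion of the two-missed-visits rule (18, or 26 after 1 year) does not fit scans that change interval at week 48, and contradicts the count rule for gaps spanning that change

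*Protocol*

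**What the plan says.** Section 8.4.3.4 first states the rule as a count: "if the subject progresses or dies after 2 or more missed visits, the subject will be censored at the time of the latest evaluable assessment". The next sentence turns that count into elapsed time: "2 missing visits will equate to more than 18 weeks (or 26 weeks after 1 year) since the previous RECIST v1.1 assessment". It adds that this allows for early and late visits. It does not say whether the 1-year mark applies to the previous assessment, the missed visits or the event.

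The scan schedule is given consistently elsewhere. Section 5.1.1 has 8-weekly scans "from first dose of study drug (Visit 2) for 48 weeks and every 12 weeks" thereafter. Section 4.2.4 agrees: "from the first dose of study drug (Visit 2) for 48 weeks, and then every 12 weeks". Each scan has a window of 1 week either side (Section 5.1.1: "If scans are performed outside of the scheduled visit ± 1 week window interval").

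A change close to 1 year does appear in the footnotes to the study plan (Table 6), but for clinic visits: "Visit to take place on Day 1 of a 4-week visit period up to 52 weeks". Tumor scans in the same table change at week 48.

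DoR (Section 8.4.3.1) takes its end date and its censoring time from PFS. TTAP (Section 8.4.3.5) uses a count of missed assessments with no conversion to weeks.

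**The concern.** The count and the week figures are presented as equivalent, and for most of follow-up they are. Around the change of interval they are not. Scans fall at weeks 40, 48, 60 and 72, so two consecutive intervals can be 8+12 or 12+12 weeks while the 18-week figure still applies. A gap starting at week 40 needs a figure that the protocol does not give.

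A programmer who follows the week figures can therefore reach a different PFS status from one who follows the count. At stake is whether a few progressions or deaths enter the PFS and DoR curves as events or as censored observations.

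**Working it through.** **Inputs.** Scheduled scans: weeks 8, 16, 24, 32, 40, 48, then 60, 72, 84 and so on (Sections 4.2.4 and 5.1.1). Window: ±1 week. Stated thresholds: more than 18 weeks, or more than 26 weeks after 1 year, taken as week 52 (Section 8.4.3.4).

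**Reproducing the stated figures.** Threshold = (second scheduled scan after the last one − last scan) + 2 weeks, the 2 weeks covering a last scan 1 week early and a later scan 1 week late.
- Constant 8-weekly: 2×8 + 2 = 18.
- Constant 12-weekly: 2×12 + 2 = 26.

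Both match.

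**The same formula along the actual schedule.**

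| Last evaluable scan | Next two scheduled scans | Threshold that matches the count |
|---|---|---|
| Week 32 (same for 8, 16, 24) | 40, 48 | 16 + 2 = 18 |
| Week 40 | 48, 60 | 20 + 2 = 22 |
| Week 48 | 60, 72 | 24 + 2 = 26 |
| Week 60 or later | 12-weekly | 24 + 2 = 26 |

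**Reading A: 1 year judged at the previous assessment.** Last scans at weeks 40 and 48 both precede week 52, so 18 weeks applies. Take exactly one missed scan, with progression at the next, and let both scans be 1 week early, on time or 1 week late (9 combinations).
- Last scan week 48, week 60 missed, progression at week 72: nominal gap 24, range 22 to 26. All exceed 18, so 9 of 9 are censored.
- Last scan week 40, week 48 missed, progression at week 60: nominal gap 20, range 18 to 22. Censored in 8 of 9. The exception is week 41 to week 59, which is exactly 18.
- Last scan at weeks 8 to 32, or at week 60 or later: 0 of 9 censored.

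**Reading B: 1 year judged at the event.** For events after week 52 the threshold is 26. Both single-miss cases (nominal gaps 24 and 20) stay events, as the count requires. The error runs the other way.
- Last scan week 32, weeks 40 and 48 missed, death or progression on an unscheduled scan at about weeks 53 to 58: gap 21 to 26, not more than 26, so kept despite two missed scans.
- Last scan week 40, weeks 48 and 60 missed, event at about weeks 61 to 66: gap 21 to 26, also kept. (A 22-week threshold would itself keep events to week 62 because of its window allowance. Measured against that threshold the excess is weeks 63 to 66.)

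**Testing remedies.** Moving the 26-week switch from 1 year to the week-48 scan corrects the week-48 case (24 ≤ 26) but not the week-40 case (20 > 18). With 18/22/26 keyed to the last evaluable scan, the largest single-miss gaps are 18, 22 and 26, none above its threshold, so no event after a single missed scan is censored.

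**The case against.** The strongest reply is that the count is the operative rule and the weeks only explain it. By count, none of the cases is ambiguous, and both printed figures are correct for a constant interval. Section 8.5.2 also leaves further detail to the SAP. Part of this stands: it shows that the simplest remedy is to say that the count governs. It does not remove the point, because the protocol commits to week figures that give a different answer from the count, and it does not say which prevails.

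Three stronger inferences are tempting and are not supported.
- *That the rule, as written, censors events after one missed scan.* This follows only under reading A, and only for a last scan at week 40 or 48. Even then the week-40 case is 8 of 9 combinations, and a progression found earlier on an unscheduled scan, within 18 weeks, remains an event.
- *That the 12-month PFS rate is overstated.* The events lost under reading A fall at about weeks 60 and 72, after week 52. Censoring at week 40 or 48 only removes those subjects from the risk set before week 52, which leaves the 12-month estimate unchanged or slightly lower. Any upward effect comes after about week 60: the later curve, the 24-month rate if it is reported, or a median beyond that point.
- *That everyone who misses one of these scans is affected.* A subject found progression-free at the next scan restarts the clock. Only those whose next evaluable result is the event are misclassified.

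**Conclusion.** The point holds as an internal contradiction with limited reach. The conversion does not match the count for gaps spanning week 48, and either reading of the 1-year mark tested here misclassifies some subjects.

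The protocol does not give the number affected, and it is probably small. As an illustration on assumed figures only: with half of a cohort of 30 to 90 subjects still at risk and 2% to 10% missing a given scan, 30×0.5×0.02 = 0.3 to 90×0.5×0.10 = 4.5 subjects per cohort would miss each of the critical scans. That is an upper bound on those misclassified at that scan.

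PFS is one of several secondary endpoints, and Section 8.5 describes the analyses as descriptive with no statistical tests. DoR is affected through its link to PFS. The primary ORR is not affected, and TTAP has no week conversion to correct. Under reading A the PFS curve may be raised after about week 60. Under reading B some events that the count rule would censor are kept.

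**What to change.** Amend the sentence in Section 8.4.3.4, and carry it into the SAP, in one of two ways.
- State that the number of consecutive missed scheduled RECIST scans governs and that any week figures are illustrative.
- Or key the threshold to the last evaluable scan: more than 18 weeks if it was at or before week 32, more than 22 weeks if it was the week-40 scan, and more than 26 weeks if it was the week-48 scan or later.

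Replacing 1 year with week 48 alone is not enough, because the week-40 gap would still be wrong. DoR follows PFS automatically and TTAP needs no change. The cost is one sentence and one programming rule, settled before database lock.

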8.4.3.5 Time to earliest progression by RECIST or CA-125, or death

The CA-125 progression will be based upon the latest GCIG guidelines. Progression or recurrence based on serum CA-125 levels will be defined on the basis of a progressive serial elevation of serum CA-125 according to the following criteria:

- Subjects with elevated CA-125 pre-treatment and normalization of CA-125 must show evidence of CA-125 \ge 2 × ULN on 2 occasions at least 1 week apart;
- Subjects with elevated CA-125 before treatment, which never normalizes, must show evidence of CA-125 \geq 2 times the nadir value on 2 occasions at least 1 week apart; or
- Subjects with CA-125 in the reference range before treatment must show evidence of CA-125 \ge 2 × ULN on 2 occasions at least 1 week apart.

Cancer antigen-125 progression will be assigned the date of the first measurement that meets the criteria as noted. Subjects are not evaluable for CA-125 if they have received mouse antibodies (unless the assay used has been shown not to be influenced by human anti-mouse antibody) or if there has been medical and/or surgical interference with their peritoneum or pleura (e.g., paracentesis) during the previous 28 days.

For the purpose of this endpoint, a subject may be declared to have PD on the basis of either the objective RECIST v1.1 criteria or the GCIG CA-125 criteria. The date of progression will be the date of the earlier of the 2 events if both are documented.

Time to earliest progression is defined as the time from the date of the first dose of olaparib until the earliest of CA-125 progression or RECIST progression, or death from any cause. Subjects without a CA-125 progression or objective radiological progression by RECIST v1.1 who are still alive at the time of analysis will be censored at their last evaluable RECIST assessment or their last available CA-125 measurement, whichever is the most recent at the time of analysis. If a subject progresses or dies after 2 or more missed RECIST and CA-125 assessments, then the subject will be censored at the time of their last evaluable assessment.

8.4.3.6 Overall survival

Overall survival is defined as the time from the date of first dose of olaparib until death due to any cause. Any subject not known to have died at the time of analysis will be censored based on the last recorded date on which the subject was known to be alive.

Assessments for survival should be made every 12 weeks following disease progression. Survival information may be obtained via telephone contact with the subject, subject's family, or the subject's current physician. Survival data will be collected at the time of database lock for ORR and again at the end of the 12-month follow-up. Survival calls will be performed in the week following the date of data cut-off for the analysis, and if subjects are confirmed to be alive or if the death date is past the data cut-off date, then these subjects will be censored at the date of data cut-off.

8.4.3.7 HRRm status

Subjects in the 2 BRCAwt cohorts (myChoice[®] HRD positive or negative) will have their HRRm status tested and will be categorized as HRRm positive or HRRm negative. Data from these 2 BRCAwt cohorts will be combined and clinical outcomes will be presented according to HRRm status (HRRm positive versus HRRm negative).

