The double-blind, placebo-controlled, Phase III NOVA trial enrolled more than 500 subjects with recurrent ovarian cancer who were in a response to their most recent platinum-based chemotherapy. This trial demonstrated that niraparib significantly prolonged PFS compared to placebo control among subjects who were gBRCAm carriers (HR = 0.27, median PFS 21.0 months vs. 5.5 months, p < 0.0001). For subjects without a gBRCAm, but whose tumors were determined to be HRD positive using the Myriad myChoice[®] HRD test, niraparib significantly prolonged PFS (HR = 0.38, median PFS 12.9 months vs. 3.8 months, p < 0.0001). Niraparib also showed statistical significance in the overall non-gBRCAm cohort, which included subjects with both myChoice[®] HRD-positive and HRD-negative tumors (HR = 0.45, median PFS 9.3 months vs. 3.9 months p < 0.0001) (TESARO 2016).

In an exploratory analysis of olaparib from Study 19 (Ledermann et al 2014), there was some evidence suggesting that the HRD assay could identify BRCAwt subjects benefiting from olaparib maintenance therapy, although numbers were small (Hodgson et al 2015). Hence, there is a rationale and some supportive data to expect an increased PFS in this subject population, but with an expectation of a potentially lower effect size.

Subjects will be recruited to this study using 2 assays, BRACAnalysis CDx[®] (gBRCA status) and myChoice[®] HRD (tumor BRCA status and HRD status), running in parallel for cohort assignment.

Homologous recombination repair mutation (HRRm) gene panel: As a secondary objective, there will be a prospective baseline analysis using a test to assess germline mutations in a panel of genes from the HRR pathway. The panel is composed of 16 HRR pathway genes: *BRCA1*, *BRCA2*, ATM, RAD51B, RAD51C, RAD54L, RAD51D, FANC/BRIP1, FANCI, FANCL, FANCN(PALB2), BARD1, CHEK1, CHEK2, CDK12, and PPP2R2A. The result of this HRRm test will not determine cohort assignment, and will only be conducted in those subjects assigned to the cohorts with BRCAwt.

Indeed, deficiencies in the HRR pathway, such as those resulting from mutations in HRR genes, may confer sensitivity to PARP inhibitors (McCabe et al 2006).

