1.2 Rationale for study design, doses, and control groups

The proposed Phase II study is designed to assess the benefit of olaparib tablets therapy in 4 cohorts of subjects with different statuses of BRCAms/HRD by assessing the efficacy (in the form of objective response) and safety of olaparib tablets monotherapy. This study will further assess the benefit of olaparib tablets in subjects beyond gBRCA, where limited evidence currently exists for benefit with the capsule formulation, i.e., in subjects with identified by myChoice[®] HRD (genetic scar) and HRRm (mutations in an identified panel of genes associated with HRR). Limited or no reported data exists for the tablet formulation in the second line treatment setting for olaparib and will be further assessed in these study populations.

Subjects will be enrolled into 1 of 4 cohorts based on gBRCA status and myChoice[®] HRD test with ORR as the primary endpoint. Homologous recombination repair mutation status relation to clinical outcome will be a secondary endpoint in this study and will be used to assess whether the gene panel additionally identified subjects who benefit from olaparib.

Secondary endpoints will also include duration of response (DoR), disease control rate (DCR), cancer antigen (CA)-125 response rate, PFS, time to any progression (TTAP, either CA-125 progression or objective progression or death), OS, mutation status of the HRRm related to clinical outcome, and safety assessments. Exploratory correlative studies will be conducted to assess potential biomarkers that correlate with clinical outcomes.

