2.2 Secondary objectives

Secondary Objectives:	Outcome Measures:
To determine the clinical effectiveness of olaparib treatment in each of 4 cohorts assessed using: • DoR, • CA-125 response rate, • DCR	• DoR, for those subjects with a confirmed response of CR or PR, response duration will be measured from the date of the measurement criteria for CR or PR are first met until the date of documented objective progression or death in the absence of disease progression.
 PFS, TTAP, OS, and 	• CA-125 response rate, defined as the percentage of subjects with a CA-125 response according to GCIG criteria divided by the number of subjects evaluable for CA-125 response.
HRRm gene panel status related to clinical outcome.	• DCR, defined as the percentage of subjects with a best overall response of confirmed CR or PR (at any time up to and including the defined analysis cut-off point) or who have demonstrated stable disease (SD) for at least 8 weeks from first dose, divided by the number of subjects in the efficacy analysis set.
	• PFS, defined as the time from the date of the first dose of olaparib to the earlier date of assessment of objective progression (per RECIST v1.1 criteria) or death by any cause in the absence of progression.
	• TTAP, defined as the time from the date of the first dose of olaparib to the earlier date of CA-125 progression (GCIG criteria) or RECIST v1.1 progression, or death by any cause in the absence of progression.
	• OS, defined as the time from the date of the first dose of olaparib to the date of death from any cause.
	• HRD status as per HRRm gene panel assessment (positive or negative) will be correlated with clinical outcome (ORR, defined above) for subjects enrolled in the 2 cohorts with BRCAwt (cohorts 3 and 4).

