5.6.1 Overview

Subjects must provide a tumor sample to be considered for the study – the sample can either be an archival sample or a new baseline tumor sample. The sample may be obtained during pre-screening (in advance of the 28-day window) upon obtaining proper consent.

The Myriad testing may be submitted in advance of the 28-day screening window if the subject consents to the appropriate pre-screening informed consent form.

For screening and cohort assignment purposes, all subjects must provide both a blood and a tumor tissue sample for Myriad central laboratory testing. All subjects must provide approximately 10 mL of blood for the prospective Myriad BRCAnalysis CDx[®] test for subjects with unknown BRCA status or for confirmation of BRCA status for those with previous results. Additionally, all subjects must provide a tumor tissue sample, minimally as 20 tumor slides, for myChoice[®] HRD screening and analysis of HRRm gene panel status.

Samples for screening and cohort assignment will be shipped directly to the Myriad central laboratory. All other blood and tumor tissue samples collected at baseline and progression will be shipped to Medpace for storage. Samples will be collected, labeled, stored, and shipped as detailed in the laboratory manual.

Prior to any cohorts being closed to enrollment, subjects may enroll in the study and initiate treatment prior to the Myriad BRACAnalysis CDx[®] and myChoice[®] HRD tests being reported; however, subjects will not be allocated into a cohort until the results are received by

the Investigator. Once the test results are received by the Investigator, the subject will be allocated into the appropriate cohort. Once a cohort reaches 90 subjects, the cohort will be closed, and subjects may not initiate treatment until their Myriad BRACAnalysis CDx[®] and myChoice[®] HRD tests are completed, the results are received by the Investigator, and it is confirmed there is an open cohort available for which the subject is eligible.

All local procedures for genetic counseling must be followed for subjects who do not know their gBRCA status at study entry.

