8.5.3 Subgroup analysis

Subgroup analyses will not be considered within individual cohorts given the limited sample size.

However, for all subjects in the 2 BRCAwt cohorts (myChoice[®] HRD positive and negative) clinical outcomes will be presented according to HRRm status (HRRm positive versus HRRm negative).

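### HRRm secondary objective: the pooled split of cohorts 3 and 4 cannot show what the panel adds beyond myChoice HRD status; separately, the test is described as germline in one section and assigned tumour slides in another

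*Protocol*

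**What the plan says.** **Analysis.** Protocol Section 2.2 lists HRRm panel status as a secondary objective, with this outcome measure: "HRD status as per HRRm gene panel assessment (positive or negative) will be correlated with clinical outcome (ORR, defined above) for subjects enrolled" in the two BRCA wild-type cohorts. Cohort 3 is myChoice HRD positive and cohort 4 is myChoice HRD negative. Section 8.4.3.7 fixes the presentation: "Data from these 2 BRCAwt cohorts will be combined and clinical outcomes will be presented according to HRRm status (HRRm positive versus HRRm negative". Section 8.5.3 repeats the pooled split as the only exception to a general exclusion: "Subgroup analyses will not be considered within individual cohorts given the limited sample size".

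**Aim.** Section 1.2 first describes assignment to cohorts by gBRCA status and the myChoice HRD test. It then says that HRRm status "will be used to assess whether the gene panel additionally identified subjects who benefit from olaparib".

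**Test.** Section 1.1 (study tests) describes a "prospective baseline analysis using a test to assess germline mutations in a panel of genes from the HRR pathway". Section 5.6.1 assigns the screening blood sample to the germline BRCA test, and says that "all subjects must provide a tumor tissue sample, minimally as 20 tumor slides, for myChoice[®] HRD screening and analysis of HRRm gene panel status".

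**The concern.** There are two separate points.

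1. When the panel is reported, the myChoice HRD result of every subject in cohorts 3 and 4 is already known. If the question is what the panel adds to that result, HRRm-positive and HRRm-negative subjects have to be compared at the same HRD status. The plan merges the two HRD groups and closes off the view within each. Both tests are presented in Section 1.1 as ways of finding repair deficiency, so their results may well be related. A pooled difference in ORR could then partly or wholly restate HRD status and be read as value of the panel.

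2. The definition of HRRm positive depends on whether the test reads germline DNA or tumour tissue. The two descriptions can put the same subject in opposite groups.

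**Working it through.** **The plan's own figure.** The protocol gives no sample size, precision or effect figure for the HRRm objective, so there is nothing to reproduce. Section 8.5 says that all analyses are descriptive.

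**Inputs.**
- Cohort size: at least 30, at most 90 (Synopsis; Section 3.5). The Synopsis considers up to 90 feasible in cohorts 3 and 4.
- ORR by HRD status: not given. Section 1.1 acknowledges a lack of ORR data for subjects characterised by the two assays. Assumed: 30% to 50% in HRD positive, 10% to 20% in HRD negative.
- HRRm prevalence by HRD status: not given. Table 4 in Section 1.1 implies 157 - 135 = 22 subjects added by the panel in Study 19 and 154 - 135 = 19 added by myChoice HRD, but not how far the two groups overlap. Assumed: 10% to 40% in HRD positive, 5% to 25% in HRD negative.

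**Formula.** Let n3 and n4 be the cohort sizes, r3 and r4 the ORRs, and p3 and p4 the HRRm prevalences. Set the HRRm effect to zero within each cohort. Then

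- pooled ORR, HRRm positive = (n3·p3·r3 + n4·p4·r4) / (n3·p3 + n4·p4)
- pooled ORR, HRRm negative = (n3·(1-p3)·r3 + n4·(1-p4)·r4) / (n3·(1-p3) + n4·(1-p4))

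**Illustration.** n3 = n4 = 90, r = 30% and 10%, p = 20% and 5%:
- HRRm positive: 18 + 4.5 = 22.5 subjects; (5.40 + 0.45) / 22.5 = 26.0%
- HRRm negative: 72 + 85.5 = 157.5 subjects; (21.60 + 8.55) / 157.5 = 19.1%
- Difference: about 7 points, with no HRRm effect in either cohort.

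**Range over wider assumptions.**

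| n3:n4 | ORR | HRRm prevalence | HRRm+ | HRRm- | Difference (points) |
|---|---|---|---|---|---|
| 30:90 | 50% / 10% | 40% / 5% | 39.1% | 17.0% | +22.1 |
| 90:90 | 40% / 10% | 25% / 10% | 31.4% | 23.6% | +7.8 |
| 30:90 | 40% / 10% | 25% / 10% | 23.6% | 16.5% | +7.1 |
| 90:30 | 40% / 10% | 25% / 10% | 36.5% | 31.4% | +5.0 |
| 90:90 | 40% / 10% | 17% / 17% | 25.0% | 25.0% | 0 |
| 90:90 | 50% / 10% | 10% / 25% | 21.4% | 31.8% | -10.4 |

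The first and last rows are the extremes of the combinations tried. The second to fourth rows differ only in enrolment mix. The difference is zero whenever p3 = p4 or r3 = r4.

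**What a split by cohort would show.** In this set-up the true difference within each cohort is zero, and a split estimates it without the mixing. The cells are small. At assumed prevalences of 25% and 10%, HRRm-positive counts are about 8 and 3 with 30 per cohort, and about 23 and 9 with 90 per cohort. Exact 95% CIs at ORRs near 30%: 2/8, 3% to 65%; 1/3, 1% to 91%; 7/23, 13% to 53%; 3/9, 7% to 70%.

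**Germline against tumour.** Take a subject in cohort 3 or 4 whose only HRR mutation is somatic. Under Section 1.1 (germline) she is HRRm negative. Under Section 5.6.1 (tumour slides) she may be HRRm positive. No visible section says which governs.

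**The case against.** Most of the case for the plan as written is sound.

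- *The formal outcome measure is met.* Section 2.2 asks for correlation of HRRm status with ORR in the two wild-type cohorts, and the pooled table gives that. A reader might infer that the plan fails its stated secondary outcome. It does not; the gap is with one reading of the aim in Section 1.2.
- *The aim can be read otherwise.* Added identification may mean beyond BRCA. Table 4 in Section 1.1 adds myChoice HRD and the panel each to BRCA mutation, never to each other. The reading against myChoice HRD rests on the preceding sentence in Section 1.2, which names that test. The wording is ambiguous, not contradictory.
- *A pooled difference need not be spurious.* On the biology in Section 1.1, defective repair leads to genomic instability, so an association of the panel with response that runs through HRD is real. What the pooled table cannot do is separate that from value beyond HRD.
- *Size and sign are assumed.* The 7 points is not an estimate. With about 22.5 HRRm-positive subjects at 26%, the approximate 95% half-width is 1.96 × √(0.26 × 0.74 / 22.5), or 18 points, so a shift of that size lies inside the noise of the table.
- *The exclusion has a reason.* Section 8.5.3 cites limited sample size, and the intervals above bear it out. In a purely descriptive study, though, this argues for showing the intervals rather than withholding the split.
- *Enrolment caps.* It is tempting to say that the 90-subject cap sets the HRD mix. It does so only if reached. The mix is nonetheless free to vary between 30 and 90 per cohort.
- *Specimen details may be in text that is not shown.* The visible part of Section 5.6 is incomplete. Sections 1.1 and 5.6.1 would still need to agree.

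**Conclusion.** Both points hold, in limited form and independently of each other.

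1. The planned HRRm presentation cannot show whether the panel adds to myChoice HRD status. This is a limit of the presentation, not of the data: both results exist for each subject. If HRRm prevalence and ORR both differ between cohorts 3 and 4, the pooled contrast mixes the two associations and shifts with the enrolment mix. With no effect within cohorts, the illustrative contrast is 26.0% against 19.1%, and about -10 to +22 points over the wider assumptions. It vanishes if either the prevalences or the ORRs are equal. Every one of these figures rests on assumed inputs.

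2. Sections 1.1 and 5.6.1 disagree on what the panel tests, and this changes who is HRRm positive. A reader might link the two points and conclude that the specimen conflict is why added value cannot be shown. It is not; the pooling alone limits that, whichever definition is used.

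**What to change.** 1. In Sections 8.4.3.7 and 8.5.3, keep the pooled table. Add, as a stated descriptive exception to the exclusion of within-cohort subgroups, ORR with exact (Clopper-Pearson) 95% CI by HRRm status within cohort 3 and within cohort 4. The cost is one table from data already collected. The drawback is small HRRm-positive cells with wide intervals, which the text should say, so that the table is not read as establishing or excluding added value.

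2. Reconcile Sections 1.1 and 5.6.1 to one specimen and one variant-origin definition of HRRm positive, fixed before the analysis. The sponsor should state which is meant. The cost is a clarified sentence in each section.
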